TITLE

Occult Paroxysmal Atrial Fibrillation in Non-Cryptogenic Ischemic Stroke

PRINCIPAL INVESTIGATOR:

[name]

CO-INVESTIGATORS:

[name], [name], [name], [name], [name]

CAMPUS:

North Shore University Hospital

INTRODUCTION/BACKGROUND MATERIAL/PRELIMINARY STUDIES AND SIGNIFICANCE

Atrial Fibrillation (AF) is an independent risk factor for stroke.¹ Between 50 and 59 years of age, 1.5% of strokes are attributed to AF, but between 80 and 89 years of age the proportion increases to 23.5%. There are 15 strokes every hour from AF.

Paroxysmal AF (PAF) is sporadic, asymptomatic and has similar risk of stroke when compared to continuous AF.^{2,3} It is not clearly defined in the literature and is more prevalent than persistent AF in patients with ischemic stroke and TIA.⁴ The incidence of paroxysmal AF in cryptogenic stroke is 1 in 6 for age > 55 and 1 in 5 for age > 75.⁵ Most studies based on the prevalence of stroke in the US would suggest that approximately 200,000 individuals may have ischemic stroke associated with PAF. We suspect this number to be higher since long-term monitoring has been restricted only to the cryptogenic stroke population. The risk of stroke recurrence is four times greater among stroke patients with newly detected AF (15.5%) compared to those with either known AF or no AF (3.9%).⁶ Some studies have shown that 5% to 30% of cryptogenic strokes may be due to undetected AF.^{7,8}

The standard Holter monitor has a low sensitivity for detecting paroxysmal AF following an ischemic stroke (approximately 5%). In the recent Crystal AF study, 30% of cryptogenic stroke patients randomized to the Reveal Insertable Cardiac Monitor were found to have PAF compared to 3% of controls over a 3 year monitoring period.^{8,9} There are numerous observational studies that support greater detection of AF with longer monitoring. (Table 1)^{10,11} Median time to AF episode detection was 84 days. Prior studies have shown that long term monitoring for detection of PAF is cost effective.¹² While the relatively high incidence of silent PAF in cryptogenic stroke patients is just now being elucidated, there is no understanding of the frequency of silent PAF in patients with a “known” or presumed etiology for their ischemic stroke other than AF. If this incidence were also found to be significant, a dramatic change in stroke evaluation and management would likely occur.

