- 24-h ECG monitoring for AF detection (eg, Holter monitor or cardiac telemetry)
- TTE and/or TEE
- CTA or MRA of head and neck
- Hypercoagulable blood panel for patients less than 55 years-old
 - Preliminary hypercoagulable work-up within 7 days will include the antiphospholipid antibody syndrome results, which will be needed to determine stroke management. All other results, which could take longer to return, including genetic tests of hypercoagulability, rarely change stroke management.

1. Have virtual CHADS2 score ≥ 3 , or
2. Have 2 or more of the following co-morbidities: obstructive sleep apnea, coronary artery disease, (Chronic Pulmonary Obstructive Disease (COPD), hyperthyroidism, BMI > 30, prior MI, prolonged PR interval (>175 ms) or renal impairment (GFR 30-60).
3. Patient or legally authorized representative who is willing to sign written consent form.
4. Patient is ≥ 40 years old (patients younger than 40 years old have a very low likelihood of having atrial fibrillation and are therefore excluded from the study).
5. Patient can have the device implanted within 10 days of the incident ischemic event

Exclusion Criteria:

1. Documented history of AF or atrial flutter.
2. Evidence of a high-risk cardiac source of embolism (LV or LA thrombus or “smoke,” emboligenic valvular lesion or tumor)
3. Untreated hyperthyroidism.
4. Myocardial infarction or coronary bypass grafting within 1 month prior to the stroke/TIA.
5. Valvular disease requiring immediate surgical intervention.
6. Permanent indication for anticoagulation at enrollment.
7. Permanent oral anticoagulation contraindication.
8. Already included in another clinical trial that will affect the objectives of this study.
9. Life expectancy is less than 1 year.
10. Pregnancy. Urine or serum pregnancy test is required for women of child bearing potential to exclude pregnancy.
11. Patient is indicated for implant with a pacemaker, ICD, CRT device, or an implantable hemodynamic monitoring system
12. Patient is not fit, or is unable or unwilling to follow the required procedures of the Clinical Investigation Plan.
13. Cryptogenic Stroke: A stroke/TIA will be considered cryptogenic if no cause is determined despite extensive inpatient workup (see Inclusion criteria) according to the standard diagnostic protocol at North Shore University Hospital

DESIGN:

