Univariate analyses will be performed to screen for potential predictors of AF. The chi-square test or Fisher’s exact test, as deemed appropriate, will be used to compare AF patients with non-AF patients for categorical variables and the two-sample t-test or Mann-Whitney test for continuous data.

As a possible secondary analysis, those factors that appear to be associated with AF in the univariate analysis ($p < 0.25$) will be included in a logistic regression model. Backwards selection will be used to remove variables that do not significantly contribute information to the model, given other factors included in the model. A receiver operating characteristic (ROC) curve will be constructed to look at the final model’s ability to predict AF. A numerical measure of the accuracy of the model will be obtained from the area under the curve (AUC), where an area of 1.0 signifies near perfect accuracy, while an area of less than 0.5 indicates that the model is worse than just flipping a coin. The following will be used as a guide for AUC:

0.9-1.0	Excellent
0.8-0.9	Very good
0.7-0.8	Good
0.6-0.7	Average
0.5-0.6	Poor

The Hosmer and Lemeshow Goodness-of-Fit test will also be used to test how well the model fits the data.

Unless otherwise specified, a result will be considered statistically significant at the $p < 0.05$ level of significance. All analyses will be performed using SAS (SAS Institute, Cary, NC).

DISCOMFORTS AND RISKS

The risks to the subjects are low in relation to the anticipated benefits of detecting paroxysmal AF, which will change the strategy of secondary stroke prevention from antiplatelet to anticoagulation

¹ Lee, E. T. (1992), *Statistical Methods for Survival Data Analysis*, Second Edition, New York: John Wiley & Sons.

² Greenwood M. (1926), *The Errors of Sampling of the Survivorship Table*, Vol. 33 of Reports on Public Health and Medical Subjects. London: Her Majesty’s Stationery Office

therapy and reduce the annual risk of recurrent stroke by allowing earlier treatment once AF is detected. The procedural risks have been reviewed under the section (“Design: Reveal LINQ Insertable Cardiac Monitor)

Potential risks and discomforts associated with receiving a Reveal LINQ ICM device include:

- Local site bleeding
- Temporary discomfort at the implant site.
- Rejection of the device by the body, which may have symptoms such as swelling, redness, or other irritation at or near the implant site

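### The committed AF-predictor tests are unadjusted and the optional model may omit age, so nothing planned shows whether a factor adds information beyond age

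*Combined protocol and SAP*

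**What the plan says.** All of the predictor analysis is in the Statistical Analysis section of the combined protocol and SAP.

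- **Committed step.** "Univariate analyses will be performed to screen for potential predictors of AF". A chi-square or Fisher's exact test "will be used to compare AF patients with non-AF patients for categorical variables", and continuous factors are compared by "the two-sample t-test or Mann-Whitney test for continuous data". No covariate is named. Unless something else is specified, p<0.05 counts as significant.
- **Optional step.** "As a possible secondary analysis", factors with univariate p<0.25 go into a logistic regression. Then "Backwards selection will be used to remove variables that do not significantly contribute information to the model". No variable is exempt from the entry screen or from removal. The final model is described by its ROC curve, AUC and a Hosmer-Lemeshow test.
- **Age in the analysis text.** It appears once, as an example of a continuous baseline variable to be summarised. The candidate predictors are not listed.
- **Age elsewhere.** The introduction puts the share of strokes attributed to AF at 1.5% for ages 50-59, and says that "between 80 and 89 years of age the proportion increases to 23.5" per cent. Inclusion item 4 sets the lower age limit at 40 because "patients younger than 40 years old have a very low likelihood of having atrial fibrillation". The introduction also gives paroxysmal AF in cryptogenic stroke as 1 in 6 above age 55 and 1 in 5 above age 75.

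**The concern.** Age is the one determinant of AF that the protocol quantifies, and several eligibility co-morbidities, such as coronary disease and renal impairment, could plausibly rise with it. If such a factor differs between AF and non-AF patients, the committed tests cannot show whether the difference is more than a difference in age. The only analysis that could show this may not be done. If it is done, age may fail the entry screen or be removed.

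At stake is the interpretation of any list of predictors. Age is known for every patient without a test, so a factor that only stands in for it adds nothing when describing which patients have occult AF. Because the model is optional, the unadjusted comparisons may be the only predictor results reported.

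**Working it through.** The plan gives no power, effect size or expected incidence for the predictor analysis, so it has no figure to reproduce. The check has three parts.

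**1. What age gradient do the documents suggest?** The introduction supports two very different answers.

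*All AF-attributed stroke, ages 50-59 to 80-89 (three decades):*
- Odds ratio = (0.235/0.765) / (0.015/0.985) = 20.2.
- Per decade: 20.2^(1/3) = 2.72.

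*Occult paroxysmal AF in cryptogenic stroke (1/6 above 55, 1/5 above 75).* The groups overlap, so assume that a share f of the over-55s is over 75.
- Rate at 55-75 = (1/6 − f/5)/(1 − f), which is 15.2% at f = 0.3 and 13.3% at f = 0.5.
- Odds above 75 are 0.20/0.80 = 0.25. The odds ratio against 55-75 is 0.25/(0.152/0.848) = 1.39 or 0.25/(0.133/0.867) = 1.63.
- If the two groups lie about 15 years apart (assumed), the per-decade value is 1.39^(2/3) = 1.25 to 1.63^(2/3) = 1.38.

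**2. How often is a pure age proxy significant?** Simulation of the committed test with N = 75 (from the protocol). Assumed, not in the documents: age mean 68 and SD 11, limited to 40-95; AF incidence 12-30%, or about 9 to 22 AF patients; a continuous factor correlated 0.3-0.5 with age that has no effect given age; two-sided 0.05. The comparison is a logistic model containing age and the factor.

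| Age OR per decade | Unadjusted t-test, p<0.05 |
|---|---|
| 1.25 | about 5-8% |
| 1.5 | about 6-13% |
| 2.0 | about 10-22% |
| 2.7 | about 11-39% |

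With age in the model the rate is about 3-6% throughout. Repeat runs moved the ends of these ranges by a few points at most. The low ends come mainly from r = 0.3 and the high ends from r = 0.5 with 30% incidence.

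**3. What happens in the optional model?** A second simulation applied the p<0.25 screen and then backward selection at p<0.05 (the removal threshold is assumed). It used AF incidence of 15-30% and an age odds ratio of 1.5 or 2.0 per SD. With an SD of 11 years these are 1.5^(10/11) = 1.45 and 2.0^(10/11) = 1.88 per decade. With r = 0.3-0.5:
- age fails the entry screen in 7-46% of trials;
- age is absent from the final model in 30-81%;
- the age proxy is retained in 4.4-7.4%, in at least half of those cases with age absent;
- with age forced in, the proxy is significant in 3.9-5.4%.

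Age is therefore often lost from the model, but the proxy is seldom kept wrongly, because the two compete when both enter. Most of the gap lies in the unadjusted tests.

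**The case against.** **A marginal association is not a false positive.** The univariate test asks whether a factor differs between AF and non-AF patients. A factor that tracks age does differ, so rejecting is correct for that question. A reader might take the percentages above as type I error of the planned tests. They are not: they count as errors only for the question of information beyond age, which the plan does not claim to answer. For pure prediction, an age proxy can be a legitimate predictor. This stands, and it limits the point to interpretation.

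**The step is a labelled screen.** A reader might infer that age-tracking factors will be declared AF predictors. The text speaks of potential predictors, gives the screen its own 0.25 threshold, and does not list predictors among the objectives. Nor do the documents say that predictors will decide who receives a monitor. This also stands. What remains is that the screen may be the only predictor result reported, with p<0.05 as its default standard.

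**The steep gradient is the less relevant one.** The 2.7 per decade describes AF-attributed stroke in general, whereas this cohort excludes known AF and AF found on inpatient monitoring. The cryptogenic-stroke figures are closer in kind, though also from another population, and at 1.25 the excess is slight.

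**The model can adjust for age.** It would be too strong to say that the plan cannot separate a factor from age: age may enter, and backward selection judges each variable given the others.

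**Hypercoagulable state.** The work-up list requires a "Hypercoagulable blood panel for patients less than 55 years-old", so this etiology might seem bound to look protective through age. The documents set a minimum and do not bar testing in older patients. Restricting the comparison to tested patients would not help much: under the assumed age distribution about 12% of 75, or 9 patients, are under 55. At 12-30% incidence that is one to three AF cases.

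**Conclusion.** The point holds in a limited form. The committed predictor analysis is unadjusted, the only adjusted analysis is optional, and age is unprotected within it. No planned result is therefore certain to show whether a factor adds information beyond age. That follows from the text alone.

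The practical size does not. It depends on the age-AF gradient, the correlation of each factor with age, and the AF incidence, none of which the documents give for this population. Near the introduction's occult-AF figures the problem is small. It becomes material at about 2.0 per decade with a factor correlated 0.5 with age. The 2.7 row is an upper bound, not an expectation.

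The incidence estimate and the Kaplan-Meier analysis are untouched. This is a modest improvement to an exploratory analysis, not a threat to the trial's main result.

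**What to change.** In the Statistical Analysis section, after the univariate tests, add wording such as: *Univariate comparisons are unadjusted and exploratory. For each candidate factor, the odds ratio for AF adjusted for age (continuous) will be reported with its 95% confidence interval. A statement that a factor predicts AF beyond age will rest on the age-adjusted result.*

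For the optional model add: *If this model is fitted, age is kept in it whatever its p-value and is exempt from the p<0.25 screen and from backward selection.* The gain from this second sentence is small.

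The cost is a few sentences and one two-variable model per factor; age is already collected. The downside is one degree of freedom and somewhat wider intervals for age-related factors, with perhaps 9 to 22 AF patients at the assumed incidences. The unadjusted results stay in the report, so a reader interested only in marginal prediction loses nothing.

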Anticoagulation is the treatment of choice for AF and paroxysmal AF.¹³ Anticoagulation in patients with paroxysmal or chronic AF reduces the risk of stroke by 64% and death by 25%.⁵ The identification of paroxysmal AF in EMBRACE (30 day) and SURPRISE (mean 133 days) led to a change in management to full anticoagulation in 13% and 18% of patients, respectively. In the Crystal AF study, 97% of patients who were diagnosed with AF were changed to oral anticoagulants.⁸ It is postulated that in the era of the novel oral anticoagulants, the detection of AF and the appropriate initiation of anticoagulation as secondary stroke prevention will reduce the risk of recurrent ischemic stroke without increasing the rates of symptomatic intracerebral hemorrhage or systemic hemorrhage. For patients with a presumed stroke mechanism other than AF who are found to have silent PAF, a change in management to full anticoagulation could have similar effects.

OBJECTIVE(S)/SPECIFIC AIMS AND HYPOTHESES

Primary Objective:

To determine the incidence of paroxysmal atrial fibrillation (AF) in ischemic stroke patients who have a presumed known stroke etiology other than atrial fibrillation.

Secondary Objectives:

- 1. Percentage of patients who are diagnosed with AF who are changed to anticoagulant therapy.**
- 2. Duration and frequency of AF episodes.**
- 3. Percentage of asymptomatic AF episodes.**
- 4. Incidence of recurrent ischemic stroke.**

SUBJECT SELECTION – ELIGIBILITY CRITERIA

The subject population will include patients with a diagnosis of Ischemic stroke. A total of 75 patients will be enrolled over a **2-year period**.

Inclusion Criteria:

Patients with a recent ischemic stroke or TIA with brain infarction on brain imaging.

1. No history of atrial fibrillation or finding of atrial fibrillation on standard inpatient monitoring (ECG, telemetry, 24-hour Holter monitor)
2. Have a presumed stroke etiology: Lacunar or small vessel thrombosis, extra-cranial or intracranial atherosclerotic stenosis or dissection, arteriopathy or vasculitis, hypercoagulable state, aortic arch plaque with or without mobile elements, or evidence of a low-risk cardiac source (e.g., PFO with or without atrial septal aneurysm and with or without evidence of venous thromboembolic source).

The following diagnostic tests are minimally required to determine the stroke etiology:

- Brain MRI
- 12-lead ECG for AF detection

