Device recording of an AF episode of at least 2 minute duration will be required to diagnose a patient with AF. A partial device transmission (summary of potential AF episodes) will be automatically downloaded daily via the Medtronic MyCareLink patient monitor and the study cardiologist will receive an alert within 24-48 hours if the computer monitoring system confirms an episode to be probable AF. Participants may also use the Reveal Patient Assistant to activate recording of cardiac information in the Reveal LINQ ICM while experiencing or immediately after a symptomatic event. Participants will be required to perform a manual device interrogation on a monthly basis. All downloaded rhythms will be manually reviewed every month for each enrolled patient by the study cardiologist. Each AF episode will also be independently adjudicated by a cardiologist blinded to the study protocol.

A total of 75 patients will be enrolled in the study. After enrollment, patients will have study visits at 1, 6, and 12 months. Six and 12 month follow-up visits will be conducted at these time intervals plus or minus 30 days. If the patient cannot come in for a follow-up visit, then the follow-up may be performed as a telephone interview. During the study visits, patients will be assessed for any interval stroke or TIA-like events, intracerebral hemorrhages, interval medical history, device related complications or other adverse events. At the 1-month visit, a NIH stroke scale score will be obtained. At each study visit, a modified Rankin score will be recorded. There will not be any research labs conducted at these study visits and only blood work associated with routine care may be obtained.

Patients will also have one EP cardiology clinical follow-up visit 10 days (plus or minus 4 days) after device implantation to ensure proper healing of the surgical site and functioning of the device.

At the completion of the study, if there is no clinical reason not to remove the device, then the device will be removed at 1 year from implantation. If there is a clinical indication for longer monitoring, then the device will be kept in longer for a maximum of 3 years. However, if clinical monitoring is required beyond the study period, then monitoring will be performed outside of the

study, and the patient or the patient's insurance will be responsible for any clinical fees associated with this post study monitoring.

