If the patient's decisional capacity is impaired, but the treating Stroke Neurologist deems the patient capable of assenting to study participation, then the patient and their LAR will be included in the informed consent process. In this case, enrollment will proceed only if the patient assents and the LAR gives consent to study enrollment. In the event that the participant is decisionally impaired to the point where both consent and assent cannot be obtained for the study, consent will be obtained from the LAR. In any other situation where the patient is deemed not to have the capacity to consent, the decision will be made not to enroll the patient in the study. All clarifications will be handled directly by the principal investigator.

The use of an LAR will be documented on the data collection form. Enrollment into the study after the informed consent process is completed will be documented in the medical record. In the event that an LAR consents on behalf of a patient lacking capacity, continuing informed consent will be obtained if the treating physician or study physician determines that the patient regains the capacity to consent during the course of the protocol. Assessment for regaining capacity to participate in the informed consent process will be performed at each study visit.

STATISTICAL ANALYSIS

Descriptive statistics (mean \pm standard deviation and median for continuous data such as age; frequencies and percentages for categorical data such as gender, medical history, etc) will be calculated for baseline patient characteristics.

The incidence of AF will be calculated as the total number of patients with AF in 12 months divided by the total number of patients studied, along with the corresponding 95% confidence interval.

The analysis of “time-to-first-documented-AF” will be accomplished by applying standard methods of survival analysis, i.e., computing the Kaplan-Meier¹ product limit curves. In cases where the endpoint event, “AF”, had not yet occurred, 12 months will be used and considered ‘censored’. The median rate will be obtained from the Kaplan-Meier/Product-Limit Estimates and its corresponding 95% confidence interval will be computed, using Greenwood’s formula² to calculate the standard error.

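### In the optional AF predictor model, a factor level with no AF cases breaks the ordinary logistic fit, and backward selection would then drop that factor if removal is by Wald test; the plan names neither the removal test nor a method for this case.

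*Combined protocol and SAP*

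**What the plan says.** The Statistical Analysis section compares patients with and without AF factor by factor, using chi-square or Fisher's exact test for categorical variables. As an optional secondary step, factors with p < 0.25 enter a logistic regression. Then "Backwards selection will be used to remove variables that do not significantly contribute information to the model". A ROC curve with its AUC, and a Hosmer-Lemeshow test, are based on the resulting model. The general significance level is 0.05, and no separate level for staying in the model is given. On software the section says "All analyses will be performed using SAS", without a procedure or options.

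The section does not say which statistic decides removal (Wald, likelihood ratio or score). It mentions no penalised or exact fit, and gives no rule for empty cells or non-convergence.

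On size, the Eligibility Criteria section says "A total of 75 patients will be enrolled", and the Follow Up section repeats the number. No expected number of AF cases is given.

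**The concern.** The two steps treat sparse data differently. Fisher's test copes with a factor level in which nobody has AF. An ordinary maximum-likelihood logistic fit does not: the log odds ratio runs off to minus or plus infinity, its standard error grows without limit, and the Wald statistic falls to about zero. A factor can therefore pass the screen as significant and then look as if it contributes nothing.

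At stake is what the multivariable model reports. A presumed etiology or co-morbidity in which monitoring finds no AF would be of real interest in this cohort. Under Wald removal the final model would omit it, and the AUC and goodness-of-fit results would describe a model without it. Under any removal test, the ordinary fit gives no finite odds ratio for it.

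**Working it through.** **Inputs.** N = 75. The outcome is read as AF by 12 months, following the primary incidence definition, "the total number of patients with AF in 12 months divided by the total number of patients studied"; the model text itself says only AF versus non-AF. The AF rate in this population is not stated. The background gives figures for cryptogenic stroke only: "Some studies have shown that 5% to 30% of cryptogenic strokes may be due to undetected AF". Applied to 75 patients, 0.05 × 75 = 3.75 and 0.30 × 75 = 22.5, so about 4 to 23 cases. The other background figure, 1 in 6, gives 75/6 = 12.5. All of these are assumptions for the present population. The stay level is taken as 0.05. The plan has no figure of its own to reproduce here.

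**Worked table: 0 of 26 with AF in one group, 9 of 49 in the rest.**

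- Fisher's exact test: p = 0.023. The factor passes the screen and is significant at 0.05.
- Wald: the variance of the log odds ratio is 1/0 + 1/26 + 1/9 + 1/40, which is infinite, so z = 0 and p is about 1. Removed.
- Ordinary likelihood ratio: 2 × [9 ln(9/49) + 40 ln(40/49) − 9 ln(9/75) − 66 ln(66/75)] = 2 × (−23.369 + 27.519) = 8.30 on 1 df, p = 0.004. Kept, but the estimated odds ratio is still zero.
- Firth: for a single binary factor the penalty adds ½ to each cell. Odds ratio = (0.5/26.5)/(9.5/40.5) = 0.080. Penalised likelihood ratio = 2 × [0.5 ln(0.5/27) + 26.5 ln(26.5/27) + 9.5 ln(9.5/50) + 40.5 ln(40.5/50) − 10 ln(10/77) − 67 ln(67/77)] = 2 × (−26.801 + 29.733) = 5.86, p = 0.015. Kept, with a finite odds ratio.

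**Iterative fits.** In 18 tables with 8, 15 or 23 cases and an empty group of 10 to 37 patients, the ordinary fit stopped at a log odds ratio of about −16 to −20 with standard error about 1,700 to 3,300. Wald p was 0.992 to 0.996 in every table, including those with Fisher p < 0.001.

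**One factor, 20,000 simulated trials per scenario** (Fisher screen at 0.25, then removal at 0.05). With 35% of patients in the group and AF in 3% against 20%, the chance of an empty group is (1 − 0.35 × 0.03)^75 = 0.45. The share of trials in which the factor reaches the final model:

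| Scenario | Wald | Firth |
|---|---|---|
| 35% share, AF 3% vs 20% | 10% | 56% |
| 35% share, AF 5% vs 25% | 26% | 62% |
| 25% share, AF 3% vs 25% | 6% | 62% |

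In the first scenario an ordinary likelihood-ratio test keeps the factor in 67%. With no true effect (35% share, AF 14% or 20%), Firth keeps it in 4.5–4.7% of trials and the ordinary likelihood-ratio test in 5.6–6.2%.

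**Small empty groups.** For 0/11 against 8/64, Fisher p = 0.59 (fails the screen) and Firth p = 0.33. For 0/10 against 15/65, Fisher p = 0.20 (passes the screen), but Firth p = 0.10, so the penalised test removes it too. With a 1/7 share and AF in 3% against 20%, an empty group with Fisher p < 0.05 occurs in 4% of trials, and Firth keeps the factor in only 10%.

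**Several factors, about 1,500 trials per scenario** (12 binary factors with assumed prevalences of 5–80%, plus one continuous). With no true effects, an empty-cell factor passes the screen in about 31%, 22% and 14% of trials at 8, 15 and 23 cases. It is the strongest factor with p < 0.05 in 3–5% of trials with no true effects, and in 1–41% with one strong true factor. Among trials with an empty-cell factor at Fisher p < 0.05, Wald removal lost such a factor every time (for example 632/632, 253/253 and 97/97 in three scenarios). Ordinary likelihood-ratio removal lost one in 2/632, 4/253 and 13/97.

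**The case against.** The strongest reply is that the plan never says Wald. It names SAS but no procedure or option, and a likelihood-ratio removal test on the same ordinary fit keeps the factor in the worked table and in nearly all affected simulated trials. That stands: the loss is conditional, and Firth is not the only way to avoid it. What the reply leaves open is that keep-or-drop then turns on an unstated choice. Ordinary likelihood-ratio removal also still leaves an odds ratio of zero or infinity, and it kept a null factor slightly too often.

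Two stronger readings are tempting. A reader might infer that the model will discard its clearest predictor. The documents do not support that: they fix no removal test and list no candidate factors, and an empty group is often small and weakly associated, so that it never enters the model. A reader might also infer that a penalised fit always retains an empty-cell factor. It does not, as the small-group tables show. Nor is a high chance of some empty cell among many small groups evidence of harm, because most such cells carry no real signal.

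It is also fair to say that the model is optional. The primary incidence and the Kaplan-Meier analysis do not use it, and the univariate table would still show a group with no AF.

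**Conclusion.** The point holds as a minor, inexpensive improvement. If a screened-in factor has a level with no AF cases or only AF cases, the planned ordinary fit gives no usable odds ratio or Wald interval. If removal is by Wald test, the factor is then dropped even when Fisher's test is significant. In the scenarios with a group of 25–35% of patients and a strong true difference, Wald removal keeps the factor in 6–26% of trials against 56–62% with Firth.

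These sizes rest on assumed group shares, AF rates and a 0.05 stay level, none of which the documents give. The mechanism in the worked table does not depend on those shares and rates. The effect largely disappears for small empty groups, and the loss of the factor, though not the unusable estimate, is largely avoided under likelihood-ratio removal. The primary and univariate results stand whatever is decided here.

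**What to change.** Replace the backward-selection sentence in the Statistical Analysis section with wording such as:

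> The multivariable model will be fitted by Firth-penalised logistic regression, and odds ratios will be given with profile penalised-likelihood 95% confidence intervals. Terms will be removed in backward selection on penalised likelihood-ratio tests, not on Wald tests.

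A factor with an empty level then gets a finite odds ratio and interval, and is kept or removed on a test that still works. Cost: two sentences and a software option. Odds ratios shrink slightly toward 1, and the removal steps must be run by hand. No further patients, visits or data are needed.
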